1. INTRODUCTION

This document outlines the proposed analyses for the NEED-PT study. Briefly, NEED-PT is a physician-randomized (i.e., physicians serve as clustering or randomization units) trial evaluating efficacy of an embedded emergency department (ED) physical therapist in comparison to usual care. Individual ED patients will be consented and enrolled during their index ED visit and will follow the randomization assignment of their treating physicians. The primary outcome data will be analyzed at three months after the index ED visit, with additional data collection up to 12 months for evaluation of longer-term effects and exploratory endpoints.

Study Aims

The overarching study aims are as follows. **This SAP will focus on the details for Aim 2 analyses, which will guide the reporting of the primary study findings.** We reserve details of analyses surrounding additional aims for separate document(s):

Aim 1: Develop and field-test the Northwestern “Embedded” ED Physical Therapy (NEED-PT) intervention protocol for the routine co-evaluation of all ED patients with acute low back pain.

We will co-locate the ED physical therapist with the ED physician as part of the primary treatment team in order to remove biases in treatment selection and allow for earlier integration of ED-PT into patient care. A formalized protocol will enhance intervention fidelity in Aim 2 and facilitate dissemination of our care model.

Aim 2: Conduct a single-center, physician-randomized trial (n=40) comparing NEED-PT to usual care among ED patients (n=360) with acute low back pain to evaluate a primary outcome of pain-related functioning at three months and a secondary outcome of opioid use at three months.

H1: Patients receiving NEED-PT will report greater improvement in pain-related functioning compared to patients receiving usual care, as measured by average PROMIS Pain-Interference score

H2: Patients receiving NEED-PT will use fewer daily opioids on average.

Aim 3: Compare rates of diagnostic imaging utilization for ED visits with low back pain among ED physicians randomized to NEED-PT versus usual care.

H1: ED physicians randomized to NEED-PT will have a lower rate of diagnostic imaging utilization for low back pain compared to ED physicians randomized to usual care.

For patients enrolled in the study, study time points include baseline assessment (completed at the index ED visit), Week 1, Month 1, Month 2, Month 3 (primary endpoint), Month 6, and Month 12.

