- 2) **Patient-Reported Opioid Use** at three months. This will be collected using a customized instrument assessing whether participants have taken any opioid medication in the last 24 hours. The 24-hour timeframe was selected to maximize accuracy in patient recall and has been used previously. In brief, opioid medications are listed by brand and generic names; a “yes” response to any medication triggers an additional query asking the participant to specify the medication dose (e.g., oxycodone 10mg) and quantity (e.g., four pills), allowing for standardization by morphine milligram equivalents (MME). We anticipate treating this variable as either count or a binary (any dose vs. none), or continuous (MME) for analyses.

Exploratory Outcomes

We expect the following outcomes to be related to the primary and the major secondary outcomes of interest. We deem the more exploratory in nature, and they thus carry less weight in analyses and overall inferences regarding efficacy of intervention.

- 1) **Opioid Prescription Filling** will be queried in the state prescription monitoring database. We anticipate treating this variable as count, binary, or continuous (MME).
- 2) **Patient-Reported Prescription Analgesic Use** in the last 24 hours will be collected using the same customized instrument described above for opioid use. Prescription analgesics include: opioids, benzodiazepines, skeletal muscle relaxants, and gabapentinoids. We anticipate treating this variable as either count or binary.
- 3) **Prescription Analgesic Filling** will be queried in the state prescription monitoring database. Prescription analgesics include: opioids, benzodiazepines, skeletal muscle relaxants, and gabapentinoids. We anticipate treating this variable as either count or binary.
- 4) **Numeric Pain Rating Scale (NPRS)** measures pain intensity from 0 to 10 and is easily understood by laypersons, clinicians, and researchers. We will assess a single item relating to average pain intensity over the last 24 hours. We plan to treat this as a continuous outcome, but we anticipate requiring transformation or nonparametric analyses, as this variable will likely be skewed and exhibit flooring / ceiling effects.

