To evaluate efficacy, the Wald model type III test for fixed arm effect will be evaluated assuming a two-sided 5% type I error rate. The primary contrast of interest to address the primary research aims involves the comparison of the model-estimated mean outcome score at three months (T4) across study arms. This modeling strategy is robust to unbalanced (i.e., incomplete) data across study time points. We will also provide results for unadjusted analyses (i.e., without accounting for the pre-specified covariates). Analyses of additional outcomes will follow the same general analytic strategy: LMM with fixed arm, baseline outcome value, influential baseline covariate effects, and a random physician effect and covariance patterns to account for repeated measures within participants. We chose to incorporate baseline outcome as a covariate in the model, rather than as a time point, based on clinical reasoning. As these baseline values (e.g., PROMIS-PI score at the index ED visit) are assessed pre-intervention and primary analyses aim to assess outcome(s) as follow-up accounting for pre-intervention state. Incorporating this baseline value in the analytic model as a fixed effect will increase precision and reduce bias on the intervention effect estimate for primary outcome at the time point of interest as the baseline value will likely be highly correlated with outcome at follow-up (previous data: $p < 0.001$ for both PROMIS and ODI).

Residual diagnostics will assess model fit and assumptions, and in the case of violation, we will explore transformations / nonparametric methods as indicated above. In the event of poor model fit, we may explore different distributional assumptions as appropriate (e.g., Poisson for count or rate data) with the corresponding canonical link (e.g., log) function. As above, we will assess model fit via residual diagnostics and may consider transforming or nonparametric methods as needed.

Analyses for outcomes that are either binary or count will follow the same general approach as above; however, they will involve generalized linear mixed effects (GLMMs) models with the appropriate distributional (e.g., binomial or Poisson) and link (e.g., logit or log) assumptions. Modeling the covariance structure for these outcomes may result in unstable model estimates. If this occurs, we anticipate removing the random physician effect and including a random participant effect instead to account for correlation.

Exploratory Analyses

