In addition to repeating the above analyses with exploratory outcomes, we will conduct exploratory analyses to study effects among subgroups of patients (moderator analyses) and examine the potential impact of PT use among patients in the control arm.

Planned moderator analyses will include the following moderators:

1. Opioid naivete as measured by whether patients report taking opioids within the last 24 hours at their index ED visit or have a history of opioid prescription filling in the Illinois prescription monitoring program within the last 3 months.
2. Initial symptom burden measured as “moderate/severe” if their baseline measures of PROMIS pain scores are ≥ 60 or their STarT score registers as “high risk,” defined as a subscore ≥ 4 (questions 5-9).
3. Age ≥ 65 years old
4. Primary treatment classification, as per the clinical care protocol (directional preference, traction, stabilization, manipulation, nociplastic presentation). As primary treatment classification is assigned only in those participants in the treatment arm (NEED-PT), we will use two approaches to study the effects of treatment classification. First, we will modify GLMM to include treatment classification effects (as opposed to just a study arm effect). Second, we will use matching methods (e.g., propensity score matching or augmented synthetic controls) to match individuals in the NEED-PT arm who have a given primary treatment classification to control arm participants on baseline covariates. We would then use GLMM to estimate the impact of each treatment classification separately.

Analyses will focus on PROMIS-PI scores measured three months after patients’ index visits, as well as ODI scores and opioid use (proportion using an opioid within the last 24 hours) at the same time point. Analyses will involve generalized linear models with appropriate link functions (identity for PROMIS-PI and logit for opioid

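### For a binary outcome, the fallback from a physician to a participant random effect can change what the logit coefficient measures, and it drops the unit of randomization

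*SAP*

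**What the plan says.** Section 2 of the SAP lists patient-reported opioid use at three months as a secondary outcome and leaves its form open: "We anticipate treating this variable as either count or a binary (any dose vs. none), or continuous (MME) for analyses".

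Section 6 gives the general model for further outcomes. It has fixed effects for arm, baseline value and covariates, with "a random physician effect and covariance patterns to account for repeated measures within participants". Binary and count outcomes follow the same approach, except that "they will involve generalized linear mixed effects (GLMMs) models with the appropriate distributional (e.g., binomial or Poisson) and link (e.g., logit or log) assumptions". The SAP then anticipates trouble: "Modeling the covariance structure for these outcomes may result in unstable model estimates". Its remedy is: "If this occurs, we anticipate removing the random physician effect and including a random participant effect instead to account for correlation".

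The SAP gives no criterion for instability. It does not say whether the effect for a binary outcome is conditional on the random effects or averaged over them. The contrast it states, written for the primary outcome, compares model-estimated means at three months between arms. In the moderator analyses of the same section, opioid use is described as the "proportion using an opioid within the last 24 hours".

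**The concern.** In a linear mixed model, a change of random effects leaves the meaning of the arm coefficient unchanged. With a logit link it does not, because the odds ratio is non-collapsible: the coefficient is conditional on whatever random effects are in the model, and it lies further from 1 as their variance grows.

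Physician variance is expected to be small, so an odds ratio conditional on physician is close to the population odds ratio. Participant variance may be large if opioid use tends to persist within the same people. An odds ratio conditional on a participant effect can then lie well away from the population value. An undefined numerical event would decide which of the two is estimated, and a reader could take a modest difference in proportions for a large effect.

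The same fallback also leaves physician clustering out of the model, so its model-based standard errors ignore the unit that was randomized.

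**Working it through.** The SAP states no rate, effect size or power for binary opioid use, so there is no figure of its own to reproduce on this point. The check asks what each model would report for the same two proportions.

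**Inputs from the SAP (Section 8).** Physician ICC of 0.01-0.04 in pilot work and 0.10 for planning; 7 participants per physician after dropout. These ICCs appear in the power section for PROMIS-PI. Carrying them over to opioid use is an assumption.

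**Assumed inputs.** Control use of 5%, 10% or 15% at month 3; population odds ratio 0.60; participant random-effect SD from 1 to 4 on the logit scale.

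**Step 1: treated proportion.** Treated odds = 0.60 × control odds. For 10% control use: 0.60 × (0.10/0.90) = 0.0667, so the treated proportion is 0.0667/1.0667 = 6.25%. The risk difference is 6.25 − 10 = −3.75 points.

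**Step 2: physician SD on the logit scale.** SD = √[ICC/(1 − ICC) × π²/3]. ICC 0.01, 0.04 and 0.10 give SD 0.18, 0.37 and 0.60.

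**Step 3: conditional odds ratio.** For each SD s, solve for the intercept η in each arm so that the mean of expit(η + s·z) over standard normal z equals that arm's proportion (Gauss-Hermite integration). The conditional odds ratio is exp(η treated − η control).

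Example at 10% versus 6.25%:
- Physician SD 0.37: exp(−2.767 + 2.251) = exp(−0.516) = 0.60.
- Participant SD 2: exp(−4.113 + 3.417) = exp(−0.696) = 0.50.
- Participant SD 3: exp(−5.365 + 4.472) = exp(−0.893) = 0.41.

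Over control use of 5-15%, with the population odds ratio held at 0.60:

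| Random effect | SD | Latent ICC | Conditional odds ratio |
|---|---|---|---|
| Physician | 0.18-0.60 | 0.01-0.10 | 0.59-0.60 |
| Participant | 1 | 0.23 | 0.57-0.59 |
| Participant | 2 | 0.55 | 0.48-0.53 |
| Participant | 3 | 0.73 | 0.39-0.44 |
| Participant | 4 | 0.83 | 0.31-0.37 |

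A second set of assumed rates gives the same picture. For 20% versus 10% the population odds ratio is 0.44, the physician-conditional value is 0.43-0.44, and the participant-conditional value is 0.40, 0.31 and 0.21 at SD 1, 2 and 3.

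**Step 4: loss of the randomized unit.** With 7 participants per physician the design effect is 1 + 6 × ICC. If clustering is ignored, the approximate two-sided type I error is 2[1 − Φ(1.96/√design effect)]:
- ICC 0.01: design effect 1.06, error 5.7%.
- ICC 0.04: design effect 1.24, error 7.8%.
- ICC 0.10: design effect 1.60, error 12.1%.

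The ICC here is on the outcome scale.

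**The case against.** Several points on the other side are sound, and they limit the concern.

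- A reader might infer that the SAP commits itself to reporting an odds ratio. It never names one. The logit link is given as an example, and the stated contrast is a model-estimated mean at three months, which for a binary outcome would naturally be read as a proportion. What stays open is whether those proportions would be averaged over the random effects.
- A reader might infer that the result would fail to answer the opioid hypothesis. That hypothesis in Section 1, "Patients receiving NEED-PT will use fewer daily opioids on average", concerns quantity. If opioid use is analysed as MME in a linear model, or as a count with a log link and random intercept, the arm coefficient is essentially collapsible and the change of meaning does not arise. The proportion is named only for the exploratory moderator analyses.
- A reader might call the fallback coefficient a within-participant effect. Arm never varies within a participant. The coefficient compares different participants who share the same random-effect value.
- The first-choice model includes a within-participant covariance pattern as well as the physician effect. If that pattern is itself fitted through participant random effects, the coefficient is already participant-specific and the swap moves it less.
- A large shift is not established. The participant SD that matters is what remains after adjustment for baseline opioid use, age, sex and STarT score. At SD 1 the shift is small.
- A reader might infer that the change of scale creates false significance. The standard error grows along with the conditional log odds ratio, so the test need not change much from this source. The type I error figures arise from dropping the physician effect, which is a different mechanism.
- Conditional odds ratios are legitimate, and the SAP promises unadjusted estimates beside the adjusted ones.

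What remains is that the swap is written into the plan, its trigger is undefined, and no summary is fixed that keeps its meaning and its physician-level inference whichever model is fitted.

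**Conclusion.** The point holds as a minor one, for outcomes analysed as binary with a logit link. The fallback can turn a near population-average odds ratio into a participant-specific one. On the assumed control rates of 5-15%, 0.60 becomes 0.57-0.59, 0.48-0.53 or 0.39-0.44 at a residual participant SD of 1, 2 or 3. Neither the rates nor the SDs come from the SAP, and the calculation takes the first-choice model to be conditional on physician only, so the shift may be anywhere from negligible to substantial.

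Separately, the fallback drops the unit of randomization. With 7 participants per physician, the approximate type I error is 5.7%, 7.8% and 12.1% at an outcome-scale ICC of 0.01, 0.04 and 0.10. Any summary taken from the fallback model therefore needs an interval that restores physician clustering.

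**What to change.** Add to Section 6, where binary outcomes are described, that whichever random effects are fitted:

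- The reported effect is the month-3 proportion in each arm and their risk difference, standardized over the covariates and averaged over the random effects.
- The confidence interval respects physician clustering, through a physician-level bootstrap or a physician-clustered robust variance with small-sample correction. A model-based delta-method interval from a participant-only model is not enough, because it would ignore the randomized unit.
- Any odds ratio is secondary and is labelled with the random effects on which it is conditional.

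This takes a few sentences in the SAP and a post-estimation step. It needs no new data and no design change. The downside is a little more computation.

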6. STATISTICAL METHODS

We plan to use descriptive statistics to summarize baseline patient and physician-level variables both overall and by arm. We will use mean±standard deviation (or median and interquartile range [IQR] as appropriate) for continuous variables and frequency / percentage for categorical variables. Specifically, we will summarize age, sex, Keele STarT score, baseline patient-reported outcome scores (PROMIS-PI and ODI), analgesic medication prescription at ED discharge, and the variables listed above. Analyses will involve normal theory methods in general, and in cases of violations of assumptions, we will consider transformation and / or nonparametric / exact methods as appropriate.

Analyses will assume a two-sided 5% significance level. All primary efficacy and safety analyses will be pre-specified as outlined in this SAP, and deviations from planned analyses or post hoc analyses will be labeled as such in any reports or dissemination materials. We do not plan to control for multiple hypothesis tests.

In analyses for each outcome, we plan to control for the respective outcome value at baseline (i.e., in an analysis of covariance [ANCOVA] approach). Analyses for the primary outcome (Y) will involve a linear mixed model (LMM) with repeated measures with fixed effects for: study arm, baseline outcome score (Y0), timepoint, timepoint-by-arm interaction, and known influential predictor effects (age, sex, Keele STarT score). Inference will focus on treatment impacts for the outcome at three months. We will include a random physician effect to account for both within and between physician variability and also to allow for estimation of the intra-cluster correlation coefficient (ICC). The repeated measures on the same participant over time will also introduce a correlation structure across time points, providing the justification for modeling the correlation structure at the

participant level over time. We will use an unstructured correlation matrix to account for the repeated measures within a participant as this has the least assumptions. If the model does not converge or parameters cannot be estimated under this unstructured covariance pattern, we will explore simpler covariance patterns using residual estimated maximum likelihood (REML) comparisons. Including repeated measures per participant will allow us to make most use of all participant data after baseline. We will use assume an unstructured covariance across time.

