use) that include fixed effects for baseline measures of the outcome of interest, treatment assignment, a moderator variable, and a treatment-moderator interaction. As above, PROMIS-PI will be modeled with standard normality assumptions, which will be evaluated via residual diagnostics and appropriate transformations will be used as necessary. Separate models will be fit for each outcome and moderator. Tests for the treatment-moderator interaction will be two-sided with a 5% type I error rate, and we will report point estimates and 95% confidence intervals. For the logistic regression involving opioid use, we will use Wald confidence intervals and Wald tests. We will not make multiple comparison adjustments.

Mediation analyses will focus on PCS and PSEQ as possible mediators. Our hypotheses are that embedding a PT in the ED can impact patients downstream pain catastrophizing and self-efficacy which will in turn lead to lower reported pain and less frequent opioid use. Our key dependent variables will be PROMIS-PI and opioid use at three months after the index visit. PCS and PSEQ measured at one month will be the mediators of interest. We will use a nonparametric approach to analyses, running separate models for each outcome and mediator (5). In addition, we will examine the possible correlation between mechanisms by using a joint nonparametric estimation framework (6).

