7. ANALYTIC DATASET

Primary and secondary outcomes will be evaluated across arms under a modified intention-to-treat (mITT) principle, (1) whereby all participants will be included in analyses, regardless of their or their physicians' adherence to their assigned study arm, and (2) only participants contributing at least one follow-up data point will be included. That is, we will exclude patients who are lost to follow-up before Week 1. Sensitivity analyses will be detailed after data collection; however, we plan to conduct sensitivity analyses that would involve:

- 1) Excluding patients who are ultimately admitted to the hospital after their ED visit. We anticipate that the number of participants meeting the criteria for this sensitivity analysis will be low. If $n \leq 10$ participants, we will combine with sensitivity analysis #2 to create a single sensitivity analysis.
- 2) Excluding patients with an alternative diagnosis after enrollment that would have deemed them otherwise ineligible (e.g., discovery of kidney stones or shingles after enrollment). We anticipate that the number of participants meeting the criteria for this sensitivity analysis will be low. If $n \leq 10$ participants, we will combine with sensitivity analysis #1 to create a single sensitivity analysis.
- 3) Excluding patients who cross over to the study arm to which they were not assigned (i.e., per-protocol analysis). If this occurs frequently, we may explore instrumental variables or propensity score methods as sensitivity analyses. This per-protocol analysis is also described in the previous section as a "complier analysis." We clarify that these two descriptions refer to the same single analysis.

Power and sample size considerations allowed for some missing data (20%). Any analysis involving missing data inherently makes assumptions about why data are missing and such assumptions are often not testable, nor are the missing data mechanisms to which they pertain necessarily known prior to the completion of data collection. Thus, we will evaluate potential missingness mechanisms and patterns that will ultimately inform multiple analyses, but we highlight here our anticipated steps and delineate possible primary and sensitivity analyses.

We will examine rates of missing data for all variables and determine whether the rates vary by participant characteristics and study arm. These summarizations will inform potential biases resulting from missing data.

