8. POWER AND SAMPLE SIZE CONSIDERATIONS

Power calculations focus on the primary endpoint of PROMIS-PI at three months, and we desire adequate (at least 80%) power to detect the minimum clinically important PROMIS-PI score difference of 3.5-5.5 points as previous literature suggests (8). If we assume a standard deviation of 10 points, which is the defined standard deviation of PROMIS-PI, this corresponds to a desired minimal detectable effect size of $d=0.35$ standard deviation unit difference across arms. Power considerations also account for a 20% drop-out rate for physician clusters (e.g., physician leaves the practice or refuses participation after randomization) and a 20% lost to follow-up rate among recruited participants. We used “The Shiny CRT Calculator” to explore varying assumptions on cluster size (i.e., average number of participants per physician), number of clusters/physicians, and ICC. Under the parallel-arm, “cohort” design, with baseline measurement of primary outcome (PROMIS), the calculator also allows for an assumption on correlation between baseline and follow-up. The table below illustrates power to detect at least a 3.5 mean difference across study arms if we assume just two time points (baseline and three months, which we deem conservative as we will have up to seven time points of observation, including baseline) per participant with a correlation between the two of approximately 0.50. We conservatively estimate that we will need to enroll up to 360 total participants to account for worst-case (20%) scenario dropout for both physicians and participants. **Thus, after accounting for physician and participant dropout, a final sample size of 16 physicians per arm and 7 participants per physician (n=224 total or 112 per arm) achieves 84% power** to detect a mean between-arm difference of 3.5 PROMIS-PI points assuming standard deviation of 10 points, ICC of 0.10, and a two-sided 5% level of significance. In our pilot work, we found a small ICC (0.01-0.04), indicating minimal within-physician effects that were not significant; however, we utilize a more conservative estimate of the ICC at 0.10 in the event that greater than anticipated within-physician effects are encountered. In the event that ICC is lower than expected or dropout rate is lower than 20%, we anticipate often over 90% to detect a meaningful difference across arms. Similar effect size in secondary outcomes (e.g., 0.35 standard deviation units difference in ODI across arms) are also detectable with at least 80% power under similar assumptions. Additionally, we plan to conduct secondary longitudinal analyses involving multiple time points per participant (i.e., more data observations) using likelihood-based methods that are robust to missing data. Therefore, we anticipate adequate power to evaluate differences across arms in outcome trajectories. **Since our target final analytic sample size is 224 total participants, if we can reach our target with fewer participants enrolled than 360, we will consider stopping enrollment.** We will plan to monitor dropout rates, ICC, standard deviation, and within-participant correlation

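### The fallback for unstable binary and count models drops the random physician effect, although physicians are the randomized unit, so the arm-effect standard error would be too small wherever patients of one physician are correlated

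*SAP*

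**What the plan says.** SAP section 1 fixes the design: "physicians serve as clustering or randomization units". Section 6 builds the main model accordingly: "We will include a random physician effect to account for both within and between physician variability". If that model fails to converge, the relief is sought in the within-participant covariance only: "we will explore simpler covariance patterns using residual estimated maximum likelihood (REML) comparisons". The physician effect stays.

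For binary and count outcomes, section 6 extends the approach to generalized linear mixed models and warns that estimates may be unstable. It then says: "If this occurs, we anticipate removing the random physician effect and including a random participant effect instead to account for correlation". Nothing else in the SAP restores physician clustering in that case.

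Whether the rule reaches the secondary opioid outcome depends on a scale that section 2 leaves open: "We anticipate treating this variable as either count or a binary (any dose vs. none), or continuous (MME) for analyses". Several exploratory outcomes are also listed as binary, count or a proportion.

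A related gap is in the Exploratory Analyses part of section 6. The models for the first three moderators are generalized linear models "that include fixed effects for baseline measures of the outcome of interest, treatment assignment, a moderator variable, and a treatment-moderator interaction", with no physician term listed. The fourth moderator, treatment classification, uses a GLMM.

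**The concern.** Arm is constant within a physician, so the arm effect is estimated entirely from differences between physicians. Its standard error must therefore include between-physician variation. The two random effects in the fallback are not interchangeable. A participant intercept absorbs the correlation among repeated visits of one patient; a physician intercept absorbs the correlation among different patients of one physician. Swapping one for the other leaves the second correlation unmodeled. For an outcome with a single value per participant, the participant effect has no repeated measures to model at all.

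The rule also runs opposite to the SAP's fallback for PROMIS-PI, which gives up participant-level structure and keeps the physician. And it sets aside the caution of section 8, where "we utilize a more conservative estimate of the ICC at 0.10" in case physician effects turn out larger than in the pilot.

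At stake are the interval and p-value for the arm effect on opioid use (H2 of Aim 2) and on the binary or count exploratory outcomes. The SAP also constrains randomization on physicians' opioid prescribing rate, so physician-level correlation in opioid outcomes is plausible.

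**Working it through.** **Inputs from the SAP.** 16 physicians per arm with 7 participants each after dropout, or 20 per arm with 9 without dropout; pilot ICC 0.01 to 0.04 and planning ICC 0.10, both for PROMIS-PI; SD 10; difference 3.5; baseline correlation 0.50; two-sided 5%.

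**Assumed, because the SAP gives no figure.** The same ICCs for opioid use; 5 to 20% users.

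**1. The plan's own power figure.** With design effect DE = 1 + (m−1)·ICC = 1 + 6·0.10 = 1.6, and a cluster autocorrelation of 1 (assumed, not stated in the SAP):

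- r = (7·0.10 + 0.90·0.50)/1.6 = 0.719
- Var = 2·10²·1.6/(16·7)·(1 − 0.719²) = 1.38, so SE = 1.175
- Power = Φ(3.5/1.175 − 1.96) = 84.6%

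This agrees with the stated 84%; with t on 30 df it is 82.2%. The sample size calculation therefore does carry physician clustering.

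**2. Dropping the physician, closed form.** The standard error without clustering is 1/√DE of the correct one, and the true type I error is 2·[1 − Φ(1.96/√DE)].

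| Patients per physician | ICC | DE | SE understated | True type I error |
|---|---|---|---|---|
| 7 | 0.01 | 1.06 | 2.9% | 5.7% |
| 7 | 0.04 | 1.24 | 10.2% | 7.8% |
| 7 | 0.10 | 1.60 | 20.9% | 12.1% |
| 9 | 0.01 | 1.08 | 3.8% | 5.9% |
| 9 | 0.04 | 1.32 | 13.0% | 8.8% |
| 9 | 0.10 | 1.80 | 25.5% | 14.4% |

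**3. Simulated binary data.** Two-proportion z test ignoring physician, 32×7 and 40×9, 5, 10 and 20% users, 40,000 replicates per cell:

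- ICC on the proportion scale (beta-binomial): 5.3 to 9.0% at ICC 0.01 to 0.04, and 11.5 to 14.5% at 0.10.
- ICC on the logit scale, 10 to 20% users: 5.2 to 7.1%, and 7.9 to 10.2%.
- ICC on the logit scale, 5% users: 4.5 to 5.6%, and 5.7 to 6.6%.
- A physician-level t test on 30 to 38 df: 4.3 to 5.2% throughout.

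**4. The fallback model itself.** Logistic GLMM with a participant intercept only, six follow-up visits, saturated arm-by-time, Wald test at Month 3; 15% users and a within-participant ICC of 0.4 assumed; physician ICC on the logit scale.

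| Physician ICC | Design | Fits | Type I error | Empirical SD / mean SE |
|---|---|---|---|---|
| about 0 | – | 972 | 5.1% | 1.03 |
| 0.04 | – | 944 | 6.6% | 1.09 |
| 0.10 | 32×7 | 958 | 9.0% | 1.17 |
| 0.10 | 40×9 | 358 | 9.8% | 1.18 |

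Monte Carlo standard error is about 0.7 to 1.6 points.

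**5. Moderator models without a physician term.** Linear PROMIS-PI model, patient-level moderator with 30% prevalence assumed, 6,000 replicates per cell. The interaction test stays at 4.6 to 5.6%. Arm effects within a subgroup run at 5.1 to 7.4% at the pilot ICC and 7.0 to 11.4% at 0.10.

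**The case against.** The strongest reply is that the harm is conditional several times over. The rule applies only if a model is unstable, only to binary or count outcomes, and only if patients of a physician are correlated. If the instability arises because the physician variance is estimated at about zero, dropping the term changes little; the simulations apply the fallback unconditionally and do not model that trigger. This stands as a limit on size. But the stated trigger is instability in general, not a zero variance, and a prespecified fallback should be valid when it is used.

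The largest figures, 12 to 14%, come from the design-effect formula and a simple z test with a deliberately cautious ICC borrowed from PROMIS-PI. The direct fit gives 9 to 10%. At ICC 0.04 its 6.6% is not clearly separated from 5.1% by Monte Carlo precision alone. Its SD-to-SE ratio is already 1.03 without clustering, so the part due to physicians is about 1.09/1.03 − 1 = 6% at ICC 0.04 and 14 to 15% at 0.10. With 5% users a Wald log-odds test starts out conservative and reaches only 3.6 to 7.5% over ICC 0.01 to 0.10. All of this is fair, and it is why a range is given.

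Constrained randomization on prescribing rate (arm means within 0.5 SD) also helps: with 20 physicians per arm it cuts the variance of the arm difference in that variable by about 39%. Even if prescribing rate explained all physician variation, a simulation with a continuous outcome still gave 7.1% at ICC 0.04 and 9.7 to 10.5% at 0.10. The constraint softens the problem and does not remove it.

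On the moderators, the objection largely succeeds. The interaction is the only test the SAP names there, and it is little affected.

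**Conclusion.** The concern holds. As written, the fallback removes the one term that represents the unit of randomization and puts nothing in its place. If it is used and patients of a physician are correlated, intervals for the arm effect will be too narrow and p-values too small.

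The size depends on quantities the SAP does not give for opioid use. Across the assumptions above, the true type I error is about 5 to 9% at the pilot ICC and about 6 to 14% at 0.10. The fallback model fitted directly gives 6.6% at ICC 0.04 and 9 to 10% at 0.10. With about 5% users and a logit-scale ICC there is little inflation.

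The primary PROMIS-PI analysis, and ODI as a continuous outcome, are unaffected. This should be fixed before analysis, but it does not threaten the primary result. The missing physician term in the moderator models is a minor point that matters only if subgroup-specific arm effects are reported.

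**What to change.** Replace the fallback sentence in section 6 with an ordered sequence in which every step keeps physician clustering:

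1. Simplify the participant-level covariance and retain the random physician effect, as is already done for PROMIS-PI.
2. If still unstable, either fit Month 3 alone with a physician random intercept, or use GEE clustered on physician with a small-sample-corrected sandwich variance and t degrees of freedom based on the number of physicians.

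As a secondary edit, add the random physician effect to the models for moderators 1 to 3.

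The cost is SAP wording and a few lines of code, with no new data. Intervals widen by √DE − 1 compared with the present fallback: about 3 to 15% at the pilot ICC and up to about 26 to 34% at 0.10 on the proportion scale. That width is uncertainty the present rule would hide. A Month 3-only fit also loses people. Section 7 defines the analysis set so that "only participants contributing at least one follow-up data point will be included", and those with follow-up but no Month 3 value would drop out. Simplifying the covariance should therefore come first.
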